- 2) Change in culturable HIV from Week -1 to Week 24;
- 3) Change in absolute CD4 T cell, CD8 T cell count and percentage as well as CD4/CD8 ratio from Week -1 to 24

3 Study Design

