4.4 Early Withdrawal of Subjects

4.4.1 When and How to Withdraw Subjects

Permanently discontinue ixazomib in individual subjects if any of the following occur:

- Death of any subject
- Anaphylactic reaction in any subject
- A life-threatening adverse event in any subject
- Any Grade 3 AE (except if there is clear evidence that it is not study drug related – i.e. a plausible alternative reason).
- Any Grade 4 AE
- A decrease in CD4 count below 350 cells/mm³, confirmed on repeat testing within 2 weeks, and associated with a relative drop in CD4 T cell percentage by >25% from baseline values, in the absence of an alternative explanation
- Confirmed virologic rebound (HIV-1 RNA >500 copies/ml confirmed by a second assay done within 14 days of the initial one). If the HIV-1 viral load is >20 copies/mL and <500 copies/mL, the HIV-1 viral load will be rechecked every 2 weeks until it becomes <20 copies/mL or >500 copies/mL.
- Development of \geq Grade 1 peripheral neuropathy with or without pain

An independent Data Safety and Monitoring Board will review the case. The committee and principal investigators will determine whether there is an association between the event and the ixazomib. The DSMB will make a recommendation accordingly as to whether the study should proceed, or if a modification in trial design is required, or if a replacement subject should be enrolled at the same dose as the withdrawn subject.

Reasons for early withdrawal of individual subjects may include:

- Subjects refuse to return for any remaining study visits.
- Subjects discontinue the ixazomib at any time during the study.
- Safety reasons, either at the discretion of the Investigator or at the subject's request.
- Protocol violations at the discretion of the principal investigators.
- Initiation of concomitant therapy that could interfere with the results of the study or ixazomib
- Subject's decision to withdraw, at any time.

All subjects are free to withdraw from participating in this study at any time and for whatever reason, specified or unspecified, and without prejudice.

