4.4.2 Data Collection and Follow-up for Withdrawn Subjects

All premature discontinuations and their causes must be carefully documented by the investigators. Subjects not completing the entire study should be fully evaluated when possible. If subjects choose to withdraw before completing the study, they should return to complete the following safety and limited efficacy assessments:

- Patient tolerability and side effects questionnaire.
- Vital signs.
- A complete physical exam.
- A review of recent clinical laboratory results, including a complete blood count, serum electrolytes, creatinine, fasting glucose, liver function tests, CD4 T cell count and HIV viral load.

If subjects who prematurely withdraw from the study do not return for this limited evaluation visit, then the relevant and available clinical data will be abstracted from the patient's medical record at the appropriate time based upon the study schedule.

Patients who withdraw from the study for virologic failure or a decrease in CD4 T cell counts will be followed until these values return to their baseline values.

5 Study Drug

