Screening for peripheral neuropathy will occur at baseline (for study exclusion), and at each study visit (for safety monitoring), by administration of the European Organization for Research and Treatment of Cancer QLQ-CIPN20 Questionnaire. The 20-item CIPN-specific questionnaire which includes three scales assessing sensory (9 items), motor (8 items), and autonomic (3 items) symptoms and functioning with each item formatted the same as items of the EORTC QLQ-C30. It was developed to be used in conjunction with the EORTC QLQ-C30 following the EORTC guidelines for module development (15911236). The EORTC QLQ-CIPN20 has been tested in cancer patients receiving a variety of chemotherapies and has been shown to have internal consistency reliability based on Cronbach's alpha coefficients of 0.82, 0.73, and 0.76 for the three scales, respectively (PMID 23543373). The questions that comprise the QLQ-CIPN20 are listed in Appendix II. Any affirmative answer to questions in the QLQ-CIPN20 will trigger a further clinical assessment, and grading of suspected peripheral neuropathy according to the (CTCAE) Version 4.0 scale (Appendix I). Further clinical assessment of suspected peripheral neuropathy will be referred to a qualified physician in the area of drug-induced peripheral neuropathy.

The following toxicities will be considered to be dose limiting toxicities:

- Any \geq Grade 4 toxicity
- Any Grade 3 AE (except if there is clear evidence that it is not ixazomib related – i.e. a plausible alternative reason).
- Any \geq Grade 1 peripheral neuropathy (PN)

Specific management of toxicities in individual participants is discussed below.

Study related biology assays for the secondary outcomes include:

- CD4 T cell count, CD8 T cell count and CD4/CD8 ratio – by routine clinical flow cytometry (Mayo Medical Labs).
- Plasma HIV RNA viral load – by routine clinical RT-qPCR (Mayo Medical Labs).
- HIV Proviral DNA – by clinical qPCR (Mayo Medical Labs)
- Cell associated HIV DNA by digital droplet PCR – Peripheral blood CD4 T cells will be isolated from baseline and post-treatment leukapheresis samples by magnetic bead negative selection. Cell associated HIV DNA will be quantified by digital droplet PCR using RainDance™ ddPCR system ([name] HIV Laboratory).

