6.16 Table 1. Table of Study Activities

Study Activity	V 1	V 2	V 3 ^c	V 3.5	V 4	V 5	V 6	V 7	V 8	V 9	V 10	V 11	V 12	V 13	V 14	V 15
Eligibility Screening	X															
Peripheral Neuropathy self-reported questionnaire	X		X		X	X	X	X	X	X	X	X	X		X	X
Informed consent	X															
Medical History	X		X		X	X	X	X	X	X	X	X	X		X	X
Concurrent meds	X															
Complete physical exam	X															
Brief physical exam			X		X	X	X	X	X	X	X	X	X		X	X
Vital Signs	X		X		X	X	X	X	X	X	X	X	X		X	X
CD4/CD8 T cell counts	X						X	X		X	X	X	X		X	X
HIV RNA Viral load	X							X		X	X	X	X		X	X
HIV Proviral DNA	X							X		X	X	X	X		X	X
CBC w/diff, platelet ^a	X		X		X	X	X	X	X	X	X	X	X	X	X	X
Heparin tubes for PBMC and plasma storage	X		X	X				X		X	X	X	X		X	
Serum chemistry ^b	X					X		X	X	X	X	X	X		X	X
Pre- and post-dose ixazomib level									X					X		
Adverse event evaluation					X	X	X	X	X	X	X	X	X		X	X
Urine Pregnancy test	X															
Leukapheresis		X												X		

a – Increased blood draw frequency may be required in the presence of hematologic toxicity. This will occur prior to each dose of ixazomib. In addition, increased blood draw frequency may be required if ixazomib is dosed weekly uninterrupted in Cycles 4-6.

b - Potassium, Creatinine, Alkaline phosphatase, ALT, AST, Total bilirubin, Direct bilirubin, Sodium, BUN, glucose, Chloride, Bicarbonate.

c- Visits 1 and 2 can occur on the same date, as long as they occur before visit 3.

6.17 Table 2: Instructions for treatment delays and dose reductions prior to ixazomib administration

CTCAE System/Organ/Class (SOC)	ADVERSE EVENT	AGENT	ACTION**
BASED ON INTERVAL ADVERSE EVENT			

CTCAE System/Organ/Class (SOC)	ADVERSE EVENT	AGENT	ACTION**
Investigations	Grade 2 thrombocytopenia (PLT count <75,000 - 50,000/mm ³) and/or neutropenia <1500 - 1000/mm ³	Ixazomib	Ixazomib dose should be omitted until the PLT and/or ANC has recovered to baseline values (counts >lower limit of normal). Ixazomib may be reinitiated at the same dose if the recovery has occurred in less than 7days. If the abnormality lasts ≥7 days or recurs, then the dose of ixazomib should be reduced by one dose level. If a patient is already at the lowest dose level, ixazomib should be permanently discontinued. Patients should have CBC checked weekly until resolution of abnormality.
	≥Grade 3 thrombocytopenia and/or neutropenia		Permanently discontinue ixazomib

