7.2 Statistical Methods

Descriptive Statistics

Univariate descriptive statistics and frequency distributions will be calculated, as appropriate for all variables. Baseline values for demographic, clinical, and outcome variables will be tabulated for the treatment groups. These analyses will help identify potential confounding variables to be used as covariates in sensitivity analyses. Putative prognostic variables that will be investigated through these descriptive analyses include variables such as age, sex, race/ethnicity, and duration of HIV infection, baseline CD4 T cell count and HIV viral load, mode of transmission, duration of ART, and duration of viral suppression.

Multiplicity

No *a priori* correction to the type I error rate is warranted for this study.

Primary Analysis

Ixazomib will be safe and well tolerated in HIV positive persons on suppressive ART.

Description statistics will be used to describe the rates of adverse effects by CTC grade of ixazomib among the dosing groups.

Secondary Analysis 1:

Ixazomib will reduce HIV DNA and replication competent viral reservoir size and improve CD4 T cell counts in HIV positive patients on suppressive ART.

To test this hypothesis, a mixed model will be estimated for each outcome separately. This model will consider linear trajectories and more flexible distribution of outcomes over time using each assessment point as a factor (i.e., a “repeated measures ANOVA formulation”). Given the limitations of the sample size, random effects for only subject (random intercept) models will be considered. These models will examine the treatment by time interaction and the linear trajectory model will be expected to have greater, but relatively poor, power to detect differences in outcomes such as viral load over time. An alpha of 0.1 or lower will be considered sufficiently significant to serve as preliminary evidence of a biologic effect to warrant further studies.

In the event the models are not able to be estimated from the data available, a planned post-hoc analysis will compare changes in secondary endpoints between participants on integrase inhibitor-based ART and non-nucleoside reverse transcriptase-based ART.

Interim Analysis

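### For the serial CD4/CD8 outcomes, the intercept-only linear model can exceed its 10% false-positive criterion if patients differ in slope or visits are serially correlated; the size depends on quantities the documents do not give

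*Combined protocol and SAP*

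**What the plan says.** Section 7.2 (Secondary Analysis 1) fits a separate mixed model to each secondary outcome, with time as a linear trajectory and also with each assessment as a factor. Because the sample is small, "random effects for only subject (random intercept) models will be considered". On the test it says: "These models will examine the treatment by time interaction". It expects the linear form to have the greater, though still poor, power. The decision criterion is: "An alpha of 0.1 or lower will be considered sufficiently significant to serve as preliminary evidence of a biologic effect". It names no random slope, residual covariance, robust variance or degrees-of-freedom method.

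Section 2 defines the immune endpoint as a change between two times: "CD8 T cell count and percentage as well as CD4/CD8 ratio from Week -1 to 24". Table 1 (6.16) schedules "CD4/CD8 T cell counts" at Visits 1, 6, 7, 9, 10, 11, 12, 14 and 15, which is 8 visits up to Week 24 and a ninth at Week 28. The reservoir outcomes differ. For ddPCR, section 6 says "Peripheral blood CD4 T cells will be isolated from baseline and post-treatment leukapheresis samples", and the outgrowth assay uses the same two collections.

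**The concern.** Dose is assigned per patient, so information about whether slopes differ by dose comes from the spread of slopes between patients. A random intercept absorbs differences in level but not in slope. If patients drift at different rates, or if nearby visits share deviations that the model treats as independent, the standard error of the interaction is too small.

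A result at 0.1 is what the plan treats as grounds for further studies. If the test rejects more often than 10% with no effect, patient-to-patient drift in CD4 or CD8 could be read as a dose effect. An intercept-only model will usually converge, so the plan's fallback for models that cannot be estimated would not flag the problem.

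**Working it through.** **Inputs from the documents.** Maximum N = 17, as 3/3/3/3 plus 5 at the maximum tolerated dose (5.2); criterion 0.1 (7.2); CD4/CD8 visits (Table 1).

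**Assumptions.** Group 5 receives 4 mg, giving dose groups 3/3/3/8. Visit 1 is placed at Week -1, so the weeks are -1, 3, 4, 8, 12, 16, 20, 24. Treatment means dose group, since 7.2 does not define it in this uncontrolled trial. Data are normal and complete. Slope SD is the SD of a patient's 24-week drift, in residual SDs.

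**Degrees of freedom.** 17 × 8 = 136 observations. Subtracting 17 patient intercepts and 4 group slopes leaves 136 − 17 − 4 = 115. Patients within groups give 17 − 4 = 13.

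**The plan's own figure.** With equal slopes and independent residuals, the linear interaction F test rejects 9.7 to 10.0% in simulation. The nominal 10% is reproduced.

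**Effect of unequal slopes.** The mean week is 10.75 and Sxx = 1466 − 8 × 10.75² = 541.5. In 24-week units this is 541.5/576 = 0.940. With slope SD τ:
- The between-patient slope mean square is k = 1 + 0.940τ².
- The model's residual mean square is (102 + 13k)/115, where 102 = 17 × 6.
- At τ = 1, k = 1.940 and the residual mean square is (102 + 25.2)/115 = 1.106. The F ratio is inflated by 1.940/1.106 = 1.75.
- The 10% critical value of F(3,115) is 2.13. Exceeding 2.13/1.75 = 1.22 has probability of about 31%.

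**Simulation, 20,000 null trials per setting, nominal 10%.**

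| Departure | Four-group by linear time | 1-df dose trend |
|---|---|---|
| Slope SD 0.25 / 0.5 / 1.0 / 1.5 | about 11 / 16 / 31 / 47% | about 11 / 13 / 21 / 29% |
| 4-week autocorrelation 0.3 / 0.5 / 0.7, pure AR(1) | about 32 / 47 / 59% | about 22 / 29 / 36% |
| Same, half the residual variance independent noise | about 21 / 27 / 32% | about 16 / 19 / 22% |
| Same, three-quarters independent noise | about 15 / 18 / 20% | about 13 to 16% |

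The serial rows assume that no serial covariance is fitted. Coding Group 5 as a separate fifth group gives 34.8% at slope SD 1.0. REML mixed-model fits (four doses, 150 trials each) gave 12.7% with no departure and 29.3% at slope SD 1.0.

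**Other analyses on the same data.** The time-as-factor form rejects about 10 to 17%. The Week -1 to 24 change, tested by dose-group ANOVA, regression on dose or one-sample t, rejects 9.4 to 10.6% throughout.

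**When the change test fails.** If the one or two patients with the worst change have no Week 24 value, the one-sample t rejects about 16% or 26% with no true effect.

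**Efficiency if the intercept-only model is right.** Over 25 weeks, the slope-based change has variance 625/541.5 = 1.154 residual variances and the two-point change has 2. The ratio is 1.154/2 = 58%.

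**The case against.** The strongest reply concerns size. Nothing in the documents shows that drift over 24 weeks is large in patients who are suppressed and enter with CD4 of at least 500, and at slope SD 0.25 the inflation is about one point. The highest serial figures need a pure AR(1) residual, which at 4-week autocorrelations of 0.3, 0.5 and 0.7 implies that Weeks 3 and 4 correlate 0.74, 0.84 and 0.91, with no independent assay or visit noise. This stands, and it is why the table shows the mild end and the noise mixtures.

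The plan is also open about its limits. It justifies the restriction by sample size, calls the power poor, makes no multiplicity correction and claims only preliminary evidence. It plans the time-as-factor form too, and does not say that the linear form alone decides. This limits the weight of the point. It does not make the linear test valid, because a small sample may rule out estimating a random slope but does not prevent a per-patient test.

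The remedy has weaknesses of its own. A mixed model keeps the early visits of patients who leave, while a change score drops them. A CD4 fall below 350, confirmed on repeat and "associated with a relative drop in CD4 T cell percentage by >25% from baseline values", is a reason to stop drug (4.4.1), so losses may depend on the outcome. A one-sample test also answers a different question from treatment by time. Both points stand and shape the fix.

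A reader might infer that the trial's real false-positive rate is 30 to 60%, or that its reservoir findings are compromised. The documents support neither. The rates are conditional on assumed values; 7.2 neither specifies nor excludes a serial covariance, and fitting one would address the second condition. The reservoir outcomes have two samples each, so the random-intercept test reduces to a change-score test.

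**Conclusion.** The point holds conditionally. For CD4, CD8 and their ratio, the linear random-intercept test of treatment by time does not protect the 0.1 criterion when slopes vary between patients, or when residuals are serially correlated and that is not modelled. Inflation of the four-group test runs from negligible (about 11%) to large (47% for slopes, 59% for pure AR(1)); the 1-df dose trend runs from 11 to 36%. Which applies cannot be known from the documents, which give no slope variance or autocorrelation. The direction is the same under every coding of treatment tried.

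The Week -1 to 24 change holds near 10% only if missing Week 24 values are unrelated to outcome. Clinical proviral DNA, also measured serially, comes into scope only if it is analysed as an outcome; it is a listed assay, not a named endpoint. This is an optional improvement to a secondary analysis and does not touch the primary safety assessment.

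**What to change.** 1. For CD4, CD8 and their ratio, base the 0.1 criterion for the treatment question on one value per patient: the Week -1 to Week 24 change already named as the endpoint, compared across dose groups or regressed on dose.
2. Report the one-sample test of that change separately, as an uncontrolled pre-post change and not as a replacement for treatment by time.
3. Keep the linear random-intercept model as a sensitivity analysis and state its residual covariance.
4. For early withdrawals, use a Week 24 value from the visit or, where 4.4.2 allows abstraction from the "medical record at the appropriate time based upon the study schedule", from that record. That route covers only patients who do not return for the limited evaluation, and the section names CD4 count but not CD8. Report losses with reasons, and add a sensitivity analysis using the last available value for patients without a Week 24 value.
5. Reconcile Visit 14 (6.14), which lists only a CD4 count, with Table 1, which lists CD4/CD8, so that the Week 24 CD8 count and ratio exist.

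**Cost.** Mostly SAP wording. P-values become less favourable, patients without a Week 24 value leave the main test, and the two-point change has about 58% of the efficiency of the slope if the intercept-only model is right. At n = 17, 80% power and two-sided 0.1, a linear dose trend must reach about 1.6 SDs of the change between 1 and 4 mg; the overall pre-post change must reach about 0.63 SD.

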AE	Adverse Event/Adverse Experience
ANC	Absolute neutrophil count
ART	Antiretroviral therapy
ARV	Antiretroviral
CFR	Code of Federal Regulations
CRF	Case Report Form
DLT	Dose limiting toxicity
DRESS Syndrome	Drug Reaction (or Rash) with Eosinophilia and Systemic Symptoms
DSMB	Data and Safety Monitoring Board
FDA	Food and Drug Administration
GCP	Good Clinical Practice
hERG	Human ether-à-go-go related gene
HIPAA	Health Insurance Portability and Accountability Act
HIV	Human Immunodeficiency Virus
IB	Investigator's Brochure
IC50	Half-maximal inhibitory concentration
IND	Investigational New Drug Application
IRB	Institutional Review Board
IV	Intravenous
LLN	Lower limit of normal
MLN2238	Ixazomib/NinLaro [®]
MM	Multiple myeloma
NCI CTCAE	National Cancer Institute Common Terminology Criteria for Adverse Events
NNRTIs	Non-nucleoside reverse transcriptase inhibitors
PHI	Protected Health Information
PI	Principal Investigator
PK	Pharmacokinetic
PN	Peripheral Neuropathy
PO	Oral administration
RBC	Red blood cell
SAE	Serious Adverse Event/Serious Adverse Experience
SCID	Severe combined immunodeficient
SOP	Standard Operating Procedure
TEN	Toxic epidermal necrolysis
ULN	Upper limit of normal
UPP	Ubiquitin-proteasome Pathway

Study Summary

Title	PILOT STUDY OF IXAZOMIB TO REDUCE THE NUMBER OF HIV DNA POSITIVE LYMPHOID CELLS
Running Title	Ixazomib for HIV cure
Protocol Number	16-001938
Phase	Phase I/II
Methodology	Dose escalation, open-label clinical trial.
Overall Study Duration	24 months
Subject Participation Duration	7 months
Single or Multi-Site	Multi-Site
Objectives	The primary objective of the trial is to determine the safety and tolerability of ixazomib in HIV positive persons on antiretroviral therapy. The secondary objective is to determine the effect of ixazomib on HIV reservoir size.
Number of Subjects	Maximum of 17
Diagnosis and Main Inclusion Criteria	Virologically suppressed HIV disease on at least 3 active drug initial or salvage antiretroviral regimens for at least 6 months

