Statistical Methodology	
This study is designed to assess the safety and tolerability of ixazomib in an HIV infected patient population, side effects will be graded according to The NCI CTCAE v4.0
 
Secondary endpoints are
 
 1) Change in HIV DNA in CD4 T cell subsets from Week -1 to Week 24; 2) Change in culturable HIV from Week -1 to Week 24; 3) Change in absolute CD4 T cell count and percentage, CD8 T cell count and percentage, and CD4/CD8 ratio from Week -1 to 24;
-------------------------	--

1 Introduction

This document is a protocol for a human research study. This study will be carried out in accordance with the applicable United States government regulations and Mayo Clinic research policies and procedures.

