3.3 Secondary Study Endpoints

Secondary endpoints will include change from baseline in measures of HIV infection (cell associated HIV DNA and culturable HIV), and immune parameters (CD4 and CD8 T cell count, as well as CD4/CD8 Ratio).

4 Subject Selection Enrollment and Withdrawal

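### Section 7.2 states a hypothesis of change from baseline, but the only contrast it names for the models is treatment by time, in a trial where everyone is treated; alpha 0.1 is tied to no term

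*Combined protocol and SAP*

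**What the plan says.** The Study Summary describes a "Dose escalation, open-label clinical trial" and lists no reference therapy; every group receives ixazomib.

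The endpoints are changes within a person. The Study Summary has "Change in HIV DNA in CD4 T cell subsets from Week -1 to Week 24", Section 2 uses the same interval, and Section 3.3 says "Secondary endpoints will include change from baseline in measures of HIV infection".

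Secondary Analysis 1 in Section 7.2 gives a directional hypothesis: "Ixazomib will reduce HIV DNA and replication competent viral reservoir size and improve CD4 T cell counts". A mixed model per outcome, with linear time or each assessment as a factor and a random intercept, is to test it. On what is examined, the text says "These models will examine the treatment by time interaction", and the sentence goes on: "the linear trajectory model will be expected to have greater, but relatively poor, power to detect differences in outcomes such as viral load over time". The threshold is: "An alpha of 0.1 or lower will be considered sufficiently significant to serve as preliminary evidence of a biologic effect". If the models cannot be estimated, "a planned post-hoc analysis will compare changes in secondary endpoints between participants on integrase inhibitor-based ART and non-nucleoside reverse transcriptase-based ART".

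**The concern.** The hypothesis is about whether an outcome moves in treated people. The named contrast is about whether it moves differently between treated subgroups. If ixazomib lowers HIV DNA equally at every dose, a dose-by-time interaction is truly zero and is declared significant only at the alpha rate, whatever the sample size. The ART-class fallback is also between groups, so no contrast named in the section answers the stated hypothesis.

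At stake is the plan's only stated rule for whether the reservoir and CD4 data justify further studies. With no term or sidedness fixed, whether the data meet alpha 0.1 depends on which coefficient is read, and that can be chosen after the results are seen. Safety and dose escalation do not depend on this analysis.

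**Working it through.** The plan gives no power figure, target effect or SD for this analysis, so there is none to reproduce. The maximum of 17 participants is the sum of the groups: 4 × 3 + 5 = 17.

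**Inputs from the documents**
- Groups of 3, 3, 3 and 3 at 1, 2, 3 and 4 mg, plus 5 at the maximum tolerated dose (Section 5.2).
- ddPCR HIV DNA from two leukapheresis samples per person (Section 6).
- Ex vivo fall of 37% (Section 1.1): log10(0.63) = −0.2007.
- Half-life of about 44 months (Summary of Hypothesis).

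**Assumptions**
- SD of the within-person log10 change of 0.2, 0.3 or 0.4.
- All 17 complete, and Group 5 is at 4 mg, so the dose levels hold 3/3/3/8.
- Two-sided alpha 0.1.

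With two samples per person, the random-intercept model reduces to an analysis of each person's change. Dose group by time is then an F test across four levels (3 and 13 df, critical value 2.56). The mean change is a one-sample t test (16 df, critical value 1.746).

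**Uniform effect.** For the mean change, the noncentrality is 0.2007 × √17 / SD = 4.14, 2.76, 2.07. For the interaction it is 0.

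**Log effect proportional to dose, 37% at 4 mg.**
- Mean dose is (3·1 + 3·2 + 3·3 + 8·4)/17 = 50/17 = 2.94 mg.
- Mean change is −0.2007 × 2.94/4 = −0.148.
- The spread of dose is Σn·d² − 50²/17 = 170 − 147.06 = 22.94.
- The F noncentrality is (0.2007/4)² × 22.94 / SD² = 0.0577/SD² = 1.44, 0.64, 0.36.
- Power of the mean change was simulated (200,000 trials), because the spread between doses adds to the estimated SD.

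| Probability of p < 0.1 | SD 0.2 | SD 0.3 | SD 0.4 |
|---|---|---|---|
| Uniform: dose group by time | 10% | 10% | 10% |
| Uniform: mean change | 99% | 84% | 63% |
| Proportional: dose group by time | 21% | 15% | 13% |
| Proportional: linear dose slope | 31.2% | 19.7% | 15.5% |
| Proportional: mean change over participants | 88% | 60% | 42% |

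**Naming the time term is not enough.** In a model with dose by time, that term can mean different things. In the proportional case, the coefficient at a 1 mg reference level (3 people) has power 13/11/11%, the unweighted mean of the four level means 72/44/30%, and the mean over participants 88/60/42%.

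**Cost of testing the mean change.** Week −1 to the Week 22 leukapheresis (Section 6.13) is 23 weeks, or 161/30.44 = 5.29 months. If the 44-month half-life applied to total HIV DNA, decay alone would give −0.301 × 5.29/44 = −0.036 log10. The noncentrality is −0.75, −0.50, −0.37. A significant fall without any drug effect then occurs in 18/12/10% of trials, against a nominal 5% in that direction.

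**The case against.** **The models already contain time.** The sentence continues to differences over time, and the endpoints are defined as change, so a sensible analyst would report the change. This stands in part. A reader might infer that the plan cannot estimate the average change, or that the interaction cannot be fitted. The documents support neither: time is in the model, and dose by time is estimable. But the clause on differences over time is a remark about power and names no test.

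**Treatment need not mean dose group.** After Day 84, Section 5.3 lets the DSMB choose the schedule person by person, and Table 2 (Section 6.17) provides for dose reductions. So it would be too strong to say that the term can only mean dose. The point survives, because every such reading still compares treated people with treated people.

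**Dose by time has a virtue that the pre-post change lacks.** A shift common to all doses, such as decay or assay drift, cannot produce it. This stands. The documents do not settle the trade-off between power and confounding, and the uniform case favours pooling by construction. It is a reason to keep dose by time as support, but not to let it stand in for the stated hypothesis.

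**It is a pilot's secondary analysis with admitted poor power.** True, and this limits the weight of the point. Low power for the right question is still different from naming another question.

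**Conclusion.** The point holds as a gap in specification that should be fixed. The named contrast and the fallback do not test the stated hypothesis or match the change-from-baseline endpoints, and alpha 0.1 has no term or sidedness.

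The figures only illustrate the size. In the assumed scenarios the interaction rejects in 10–21% of trials and the mean change in 42–99%. They rest on assumed SDs, full completion of a maximum sample, Group 5 at 4 mg and an ex vivo effect. They apply to the two-sample ddPCR outcome, not to the repeatedly measured proviral DNA or CD4 counts.

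A reader might also infer that a significant mean change would show a drug effect. Without a control group it would not: natural decay, assay drift and regression to the mean are mixed into it.

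**What to change.** In Section 7.2:

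1. Define treatment as the assigned starting dose level, with Group 5 pooled with the level it repeats. Note that later schedule changes (Section 5.3) and dose reductions (Table 2) are not part of that factor.
2. For each outcome, name the within-person change from baseline averaged over all participants, with a 90% CI, as the term to which two-sided alpha 0.1 applies. Say explicitly that this is not the time coefficient at a reference dose. State the time point, and reconcile the Week 24 endpoint with the Week 22 leukapheresis here, in the Study Summary and in Section 2.
3. Keep dose by time as supportive evidence.
4. Make a paired t or signed-rank test of change the fallback, and label the ART-class comparison exploratory.

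Choosing a lead HIV DNA assay, fixing a value for negative cultures and reporting expected decay are optional additions.

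The cost is wording in Section 7.2, plus the time-point reconciliation in the Study Summary and Section 2; no new data or participants are needed. The downside is the confounding of an uncontrolled pre-post change, and an average that depends on the dose level at which Group 5 is treated. The result must therefore be reported as preliminary evidence only.
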